9 DEVICE DEFICIENCY REPORTING

[figure not shown]
9.1 INVESTIGATOR RESPONSIBILITY

Product Defect is the terminology typically used in contact lens products for an unexpected observation related to the identity, quality, durability, reliability, or usability of the product under investigation. Any defective lens that is *likely* to cause or contribute to a *Serious Adverse Event* should be reported to the Principal Investigator and the sponsor **within 24 hours** of the investigator becoming aware of the malfunction. The ORE would also be notified within 24 hours of any device malfunction that may contribute to a *Serious Adverse Event*.

Other defective lenses should be reported to the Sponsor as soon as possible but no later than 5 working days are occurrence.

Note: Observations on study products that are anticipated as a part of the device development process are not considered to be Product Defects or Device Deficiencies.

If the Product Defect is associated with an adverse event, the investigator shall report the Product defect via the CooperVision Adverse Event Notification Form. If the Product Defect is not associated with an adverse event, the investigator shall report the Product Defect via the Clinical Product Defect Notification Case Report Form. Sponsor contact details **for Product Defect Notifications** are:

9.2 SPONSOR RESPONSIBILITY

Device Deficiency is defined as the inadequacy of a medical device with respect to its identity, quality, durability, reliability, usability, safety or performance.

The Sponsor will review the Product Defect Notification Case Report Form, gather additional information if needed from the Investigator/CRO and determine whether the notification represents a Device Deficiency. Device Deficiencies will be reported as per Internal CVI procedures.

A summary of Device Deficiencies will be documented in the clinical study report. If no Device Deficiencies are observed in a study, then a statement stating as such will be included in the clinical study report.

10 STUDY COMPLETION AND REMUNERATION

At the last scheduled protocol visit a study completion form will be completed, which requires the signatures of both the participant and the investigator. Once their involvement in the study is complete, participants will be informed about receiving feedback following study completion in the Letter of Appreciation. Participant remuneration will be \$20 per scheduled protocol visit hour (including the initial screening visit). Full details are given in the information consent letter.

11 STATISTICAL ANALYSIS AND DATA MANAGEMENT

11.1 STATISTICAL ANALYSIS

All study data will be analyzed by CORE at the University of Waterloo. Summary statistics will be produced (e.g. mean, standard deviation). Data analysis will be conducted using Statistica and / or SPSS, or other appropriate software. Descriptive statistics will be provided on information regarding baseline demographic variables (age, sex, refractive error distribution, etc.). Table 6 lists the primary outcome and other variables and anticipated statistical procedures. All data will be tested for normality of distribution using Shapiro-Wilk tests.

A binomial test will be used to analyze the results for the count data of subjective preferences. The number of “no preference” responses will be evenly distributed to the two options on the basis they would be equally likely to choose either.

The critical alpha level for statistical significance will be set at 0.05.

For assessments conducted for each eye separately, the right eye will be used for analysis. If a general difference is found (paired t-test / Wilcoxon matched pairs) between OD and OS, a comment will be provided.

All participants who completed the study will be used in the analysis, unless exclusion agreed with the sponsor based on protocol deviation or adverse event information. In the event of missing data, individual data points will not be extrapolated from the collected data.

Table 6: Outcome variables and anticipated statistical procedures

Variable	Analysis	Statistical test
Subjective ratings, Primary outcome: binocular subjective rating of the ease of lens application to eye	Descriptive and other statistics	Mean, Median, Standard Deviation, Minimum, Maximum, Frequency count
	Effect of study treatment (comparison between study lenses)	Paired t-test Wilcoxon matched pairs test Friedman

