2 OBJECTIVES

The objective of this investigation is to evaluate subjective ratings of lens handling at insertion, specifically subjective rating of the ease of lens application to eye by participants for two CooperVision lenses, clariti elite versus Proclear 1 day, in habitual soft lens wearers.

The primary outcome variable for this study is:

- Subjective rating of ease of lens application to eye (0-100, integer steps)

The other outcome variable for this study is:

- [REDACTED]

[figure not shown]

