4.2 STUDY POPULATION

4.2.1 SAMPLE SIZE CALCULATION

Sample size: The target sample size for this study is 30 participants to be randomized and to wear both lens types. This target was determined based on the sample size calculation below:

Based on previous data for "lens handling for removal" which showed a standard deviation of the difference between means of 18 points (0-100 scale), a minimum sample size of 28 is required to detect a paired difference between groups of 10 units on a 0-100 scale with 80% power and alpha 0.05 in a two-tailed t-test.

Therefore, in this study, a maximum of 30 participants to be randomized and wear both lens types.

11. Have undergone refractive error surgery or intraocular surgery;
12. Are a member of CORE directly involved in the study.

* For the purposes of this study, active ocular disease is defined as infection or inflammation which requires therapeutic treatment. Mild (i.e. not considered clinically relevant) lid abnormalities (blepharitis, meibomian gland dysfunction, papillae), corneal and conjunctival staining and dry eye are not considered active ocular disease. Neovascularization and corneal scars are the result of previous hypoxia, infection or inflammation and are therefore not active.

* Any potential exclusion will be reviewed with the Lead Investigator or Principal Investigator prior to final decision making.

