4.6.12 QUESTIONNAIRES AND SUBJECTIVE RATINGS

Subjective ratings:

[figure not shown]
After lens insertion at visits 2 and 3, participants will be asked to complete questionnaires for binocular subjective ratings (0-100, integer steps) related to:

- i) Ease of blister pack opening,
- ii) Lens stability on fingertip
- iii) Ease of lens application to eye (key outcome)

At the end of visit 3 after removing lens pair 2, participant will be asked to complete a 5-point Likert preference questionnaire (to select one of the following answers for each question: prefer Lens pair #1 strongly, prefer Lens pair #1 slightly, No preference, prefer Lens pair #2 slightly, prefer Lens pair #2 strongly) binocularly related to:

- i) Overall lens handling at insertion
- ii) Overall lens handling at removal
- iii) Overall lens handling experience

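### Splitting no-preference answers evenly before a binomial test on all answers overstates the null variance, costs power when ties are many, and cannot be run as written when the tie count is odd

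*Combined protocol and SAP*

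**What the plan says.** Section 4.6.12 asks three preference questions at the end of visit 3: lens handling at insertion, at removal, and overall. Each has five options: "prefer Lens pair #1 strongly, prefer Lens pair #1 slightly, No preference, prefer Lens pair #2 slightly, prefer Lens pair #2 strongly".

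Section 11.1 gives the analysis: "A binomial test will be used to analyze the results for the count data of subjective preferences". It adds that no-preference "responses will be evenly distributed to the two options on the basis they would be equally likely to choose either". It also states that "The critical alpha level for statistical significance will be set at 0.05".

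Section 4.2.1 sets "a maximum of 30 participants to be randomized and wear both lens types", and section 11.1 analyses completers, so N is 30 or slightly fewer. The visible text does not say whether the binomial test is two-sided, what happens when the number of no-preference answers is odd, or whether the result will also be given with those answers left out.

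**The concern.** A binomial test on N answers treats every answer as an independent 50:50 choice. The stated justification, that undecided participants would be equally likely to pick either lens, describes that kind of random choice. The rule actually applied is a fixed half-and-half division, which contributes no randomness. Rationale and method therefore do not match, and the test judges the observed imbalance against too wide a null distribution.

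Two things are at stake. With many ties, a real preference can be reported as non-significant and read as equal handling. With an odd number of ties, the analyst must decide after seeing the data where the spare answer goes, and near the significance boundary that decision settles the result.

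**Working it through.** **Inputs.** N = 30 (section 4.2.1) and alpha 0.05 (section 11.1). Two-sided testing is an assumption, in line with the two-tailed sample size calculation. The documents give no tie rate and no expected strength of preference, so those are assumed and shown over a range.

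**The plan's own figure.** The documents give no calculation for the preference test. The primary sample size does reproduce: with SD 18 and a difference of 10, the noncentral t gives power 79.4% at n = 27 and 80.9% at n = 28, so the minimum is 28 as stated.

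**Variance.** Given T ties, let X be the number preferring lens A among the N−T who state a preference. Under the null, X ~ Binomial(N−T, ½). The plan tests Y = X + T/2 as if Y ~ Binomial(N, ½).
- Assumed variance: N/4.
- True variance: Var(X) = (N−T)/4.
- Ratio at N = 30: 20/30 = 67% at T = 10, and 15/30 = 50% at T = 15.

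**Critical value.** The exact two-sided p-value is 2 × P(Bin(n, ½) ≥ k). For 21 of 30, p = 0.043; for 20 of 30, p = 0.099. The split count must therefore reach 21 v 9.

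**Even tie counts.** Over all outcomes, the plan's p-value is never below the sign-test p-value. No 0.05 decision differs at 0 to 8 ties. At every even count from 10 to 24, at least one differs. Examples:

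| Stated preferences | Ties | After split | Plan p | Sign test p |
|---|---|---|---|---|
| 15 v 5 | 10 | 20 v 10 | 0.099 | 0.041 |
| 14 v 4 | 12 | 20 v 10 | 0.099 | 0.031 |
| 10 v 0 | 20 | 20 v 10 | 0.099 | 0.002 |

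**Odd tie counts.** Each outcome below splits to 20.5 v 9.5. Rounding gives 21 of 30 (p = 0.043) if the spare answer goes to the leading lens, or 20 of 30 (p = 0.099) if it goes to the trailing lens.

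| Stated preferences | Ties | Sign test p | Possible error under the split |
|---|---|---|---|
| 20 v 9 | 1 | 0.061 | significance gained (spare to leader) |
| 19 v 8 | 3 | 0.052 | significance gained (spare to leader) |
| 18 v 7 | 5 | 0.043 | significance lost (spare to trailer) |
| 17 v 6 | 7 | 0.035 | significance lost (spare to trailer) |
| 16 v 5 | 9 | 0.027 | significance lost (spare to trailer) |

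If the spare answer always goes to the leader, conditional type I error is 6.1% at 1 tie and 5.2% at 3 ties.

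**Averaged over assumed tie rates, N = 30.** Ranges run from spare-to-trailer to spare-to-leader. Power is for a 75:25 preference among those who state one.

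| Tie rate | Plan size | Sign test size | Plan power | Sign test power |
|---|---|---|---|---|
| 10% | 2.6–4.2% | 2.9% | 68–75% | 70% |
| 20% | 1.8–3.1% | about 3% | 56–64% | 64% |
| 30% | 1.1–2.1% | 2.9% | 41–51% | 57% |
| 40% | 0.6–1.3% | 3.0% | 26–36% | 50% |
| 50% | 0.3–0.6% | 2.8% | 13–20% | 41% |

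The width of each plan-power range is the share of trials in which the spare answer alone decides significance, about 7–10%. The chance of 10 or more ties among 30 is 6% at a 20% tie rate, 41% at 30% and 82% at 40%.

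**The case against.** The strongest reply is that this is a side endpoint and the rule errs on the safe side. The hypothesis, the visible primary outcome and the sample size all concern the 0–100 rating of lens application, which has its own tests in Table 6. The split is prespecified and keeps every respondent in the denominator, whereas the sign test speaks only for those with a preference.

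The false-positive figures above 5% are conditional on an exact tie count and an unfavourable rounding rule that the plan does not state. Under that same rule, overall size at N = 30 peaks at 4.9%, near a 3% tie rate. With fewer completers, conditional size at 1 tie is 3.6% (N = 29), 5.2% (N = 28), 2.9% (N = 27) or 4.3% (N = 26).

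The 7–10% share belongs to the 75:25 scenario. With no true preference it is about 0.4–1.7%, and at 60:40 about 1–4.5%. The large power losses need tie rates of 30% or more, which nobody can confirm in advance. A rule for the spare answer could also stand in text that is not available here.

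Most of this stands as a limit on size: overall type I error is controlled, the primary analysis is untouched, and with few ties little power is lost. It does not remove the defect. Being conservative does not help with an odd tie count, which occurs about half the time and for which the visible rule gives no admissible count. Nor is conservatism harmless when a missed preference may be read as equal handling.

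**Conclusion.** The concern holds: the rule is wrong as written and should be fixed. The test uses null variance N/4 where the fixed split gives (N−T)/4. For even tie counts this yields a valid but conservative test, with no effect on decisions up to 8 ties in 30 and a growing loss of power from 10. For odd tie counts the rule cannot be applied without a further choice, and at 20.5 v 9.5 that choice moves p between 0.043 and 0.099, either gaining or losing significance relative to the sign test.

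The variance result and the p-values are exact for N = 30 with a two-sided test. The power figures rest on assumed tie rates and a 75:25 preference. The point is confined to the three preference questions, whose formal rank cannot be seen because of redaction.

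**What to change.** Before unmasking, replace the splitting sentence in section 11.1 with wording such as:

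> *Preferences will be recoded from pair #1/#2 to lens type. An exact two-sided binomial (sign) test will be run on participants who state a preference. The number and percentage with no preference will always be reported beside it.*

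An exact Wilcoxon signed-rank test on the five options scored −2 to +2 is a reasonable alternative, provided the handling of zeros is stated. If the sponsor prefers to keep the split, the plan should say in advance where the spare answer goes when the tie count is odd, and acknowledge that the test is conservative when ties are many.

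The cost is one sentence of analysis text, with no new data or procedures. The one drawback is that the p-value then refers only to participants with a preference. A result of 6 v 0 with 24 ties would give p = 0.031 and must be read with the 24 of 30 (80%) who had none, which is why that share should always be reported.

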4.4.3 LENS 1 WEAR PERIOD (V2)

The Screening Visit (V1) will be immediately followed by Lens 1 Wear Period (V2) on the same day.

Visit procedures:

1. Participant will be assigned a randomization ID (by the study research assistant/unmasked staff)
2. Lens pair #1 will be provided to participants in a manner, which does not unmask the participant or investigator, as described in Section 4.3.5.
3. Participant to open blister packs and apply the Lens pair 1 OU – [REDACTED]
[REDACTED]
4. The participant will be asked to provide binocular subjective ratings at insertion for the following (0-100, integer steps):
 - i) Ease of blister pack opening
 - ii) CL stability on fingertip
 - iii) Ease of CL application to eye
5. [REDACTED]
6. [REDACTED]
7. [REDACTED]
8. [REDACTED]
9. [REDACTED]
10. [REDACTED]
11. [REDACTED]
12. [REDACTED]
13. The participant will remove the lenses.

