8 DISCONTINUATION FROM THE STUDY

Participants may be discontinued at the discretion of the investigator or sponsor in consideration of participant safety or protocol compliance, or at discretion of the participant. Participants discontinued from a study will be reimbursed \$20 per hour for their in-office visits (including the initial screening visit). Upon discontinuing, a participant will be offered the option of their data being withdrawn from future statistical analysis. The following is a list of possible reasons for discontinuation from the study:

- Screening failure: Participants will be discontinued if they do not meet the inclusion and exclusion criteria outlined in section 4.2.3.
- Unacceptable performance with products to be used in study: Participants may be discontinued if they are unable to achieve acceptable fit, comfort and /or vision with the study products.
- Positive slit lamp finding: Participants may be permanently discontinued from the study depending on the severity of the condition and on the judgement of the investigator.
- Adverse event: If a participant experiences an adverse event during the study they may be discontinued based on the clinical judgement of the investigator.
- Symptoms: If the participant has persistent symptoms they may be discontinued based on the clinical judgement of the investigator.
- Violation of protocol or non-compliance: The participant will be discontinued if they are unable or unwilling to follow the protocol specified visit schedules and/or study procedures.
- Instillation of topical ocular medication: The participant will be discontinued if they elect to use a topical ocular medication during the study.
- Lost to follow-up: The participant will be discontinued if they cannot be contacted and do not return for a final exit visit, and if the investigator has made a reasonable effort to contact the participant for a final study visit.
- Premature termination of the study by the sponsor, CORE or the Office of Research Ethics at the University of Waterloo.

A discontinuation form, stating the reason for discontinuation will be completed, which requires the signatures of both the participant and the investigator except where the participant is lost to follow-up in which case only the signature of the investigator is required.

All discontinuations including their reasons will be included in the final report.

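### The primary rating is given at insertion, but section 11.1 bases the analysis on study completers, so a participant with both ratings can be dropped for a later event

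*Combined protocol and SAP*

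**What the plan says.** - **Analysis population (section 11.1):** "All participants who completed the study will be used in the analysis", with a further carve-out "unless exclusion agreed with the sponsor based on protocol deviation or adverse event information". On gaps it says: "In the event of missing data, individual data points will not be extrapolated from the collected data". The visible text defines no other analysis set.
- **Primary test (section 11.1, Table 6):** "Paired t-test Wilcoxon matched pairs test Friedman". A comparison of two lenses within participant needs a rating for each.
- **Timing of the primary rating:** section 4.4.3, step 4, says "The participant will be asked to provide binocular subjective ratings at insertion for the following (0-100, integer steps", and section 4.4.4 repeats that step for the second lens. Section 4.6.12 says "After lens insertion at visits 2 and 3, participants will be asked to complete questionnaires for binocular subjective ratings".
- **What follows the rating:** wear of about 90 minutes per lens (section 4.3.1), removal (4.4.3, step 13), the preference questionnaire (4.4.4) and the exit visit (4.4.5).
- **Completion:** section 4.4.5 treats completing the study and being discontinued as alternatives. Section 10 ties the completion form to the last scheduled visit.
- **Discontinuation (section 8):** "Participants may be discontinued if they are unable to achieve acceptable fit, comfort and /or vision with the study products". Symptoms, slit-lamp findings and adverse events are also listed. A participant who discontinues is offered the option of having their data withdrawn from later statistical analysis.

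**The concern.** The primary outcome is fixed once the second lens has been rated. Nothing after that can change it, but it can still decide whether the participant counts. Someone who stops during wear of the second lens because of comfort, vision, symptoms or a slit-lamp finding has a valid paired difference. Completion-based membership discards it for reasons that arose after measurement. This happens by rule and is separate from exclusions agreed with the sponsor.

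A second, less certain matter concerns application itself. The rating is requested after insertion. If a participant cannot get a lens onto the eye, the visible text provides no rating and no record of success or failure. That would be the worst possible result on the quantity being measured, and leaving it out would tend to make the harder-to-apply lens look easier.

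**Working it through.** **1. The plan's own sample size.** Inputs from section 4.2.1: difference 10, SD of the paired difference 18, two-sided alpha 0.05, power 80%, minimum 28, maximum 30 randomised.

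Power = P(|T| > t(0.975, n−1)), where T is noncentral t with n−1 degrees of freedom and noncentrality (10/18)·√n.

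| Pairs analysed | Noncentrality | Power |
|---|---|---|
| 30 | 3.04 | 0.837 |
| 29 | 2.99 | 0.823 |
| 28 | 2.94 | 0.809 |
| 27 | 2.89 | 0.794 |

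The smallest n with power of at least 0.80 is 28, so the plan's figure reproduces exactly. The margin is 30 − 28 = 2 pairs (2/30 = 6.7%). Each lost pair costs about 0.014 to 0.015 in power. The visible text states no replacement rule.

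**2. Who is lost under a completer rule, by time of stopping.**

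| Stops | Both ratings exist? | In a completer set? | In a both-ratings set? |
|---|---|---|---|
| Before the second rating | No | No | No |
| After the second rating, before the end of V4 | Yes | No | Yes |
| Completes V4 | Yes | Yes | Yes |

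The two sets differ only in the middle row. There the paired difference is observed and needs no imputation, so keeping it does not conflict with the missing-data rule.

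**3. Section 11.1 beside section 8.** Section 11.1 names completers as those to be used. Section 8 gives a discontinued participant the choice of withdrawing data from later analysis, and that choice has little purpose if such data are never analysed. Neither section settles the middle row.

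**4. Failed applications: direction only.** The documents give no failure rate, so these figures are assumptions. Suppose the mean difference over all 30 would be −10, and k participants who failed with the harder lens would have a difference D. The mean among the rest is (−300 − kD)/(30 − k).

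- k = 1: D = −30 gives −270/29 = −9.3; D = −80 gives −220/29 = −7.6.
- k = 2: D = −30 gives −240/28 = −8.6; D = −80 gives −140/28 = −5.0.

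The observed difference shrinks towards zero. With no failures there is no effect.

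**5. How influential an assigned failure score is.** Add one pair with difference −80 (a 0 against an 80) to 29 pairs with mean 10 and SD 18.

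- Mean: (290 − 80)/30 = 7.0.
- Sum of squares: 28·18² + 29·(10 − 7)² + (−80 − 7)² = 9,072 + 261 + 7,569 = 16,902.
- SD: √(16,902/29) = 24.1.

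One assigned value moves the mean by 3 points and raises the SD from 18 to 24.1. That is too much for a convention in the primary analysis.

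**The case against.** **Section 11.1 does not say that only completers are analysed.** It says that they will be used, and the data-withdrawal option in section 8 suggests that discontinued participants' data are otherwise kept. This stands in part: exclusion is the natural reading but not the only one. It makes the case for reconciling the sections, because the choice should not be left until the data are in hand.

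**A reader might infer that a participant who cannot apply a lens must be discontinued and is never scored.** The documents do not support this. Part of step 3 of section 4.4.3 (the application step) and all of steps 5 to 12 are redacted, and a rule on failed or repeated attempts may sit there. Section 8 is a list of possible reasons. The mandatory wording, "The participant will be discontinued if they are unable or unwilling to follow the protocol specified visit schedules and/or study procedures", appears under non-compliance, while a failed application fits at least as well under unacceptable product performance, where discontinuation is optional. A difficult application that finally succeeds is still rated.

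**A reader might infer that the completer result is biased by a known and large amount.** This is not supported either. Nothing links later discomfort, poor vision or a slit-lamp finding to the application rating already given, so the direction is unknown for those drop-outs. For failed applications the direction is plausible, but the size rests on assumed values.

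**Losses should be rare, and they will be visible.** Participants are habitual soft lens wearers attending for one four-hour day, and section 8 has all discontinuations and their reasons reported. This stands, and it limits the likely size. It does not justify discarding pairs that are complete.

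**Conclusion.** The point holds for participants who have rated both lenses and then stop. Their primary outcome is complete, the natural reading of section 11.1 drops it, and section 8 points the other way. The firm harm is lost valid data, up to two pairs before power falls below the planned 80% (0.809 at 28, 0.794 at 27), assuming the plan's SD of 18, a difference of 10 and no replacement of losses.

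The failed-application part is secondary and conditional. It applies only if the redacted steps of section 4.4.3 contain no rule for a failed attempt. If so, the omission would tend to favour the harder-to-apply lens, by an amount that the documents do not allow one to estimate.

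The sample size calculation is not at fault. With no losses, the result is the same under either definition. The change is worth making because it costs almost nothing and fixes the rule in advance.

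**What to change.** 1. **Section 11.1:** define the primary analysis set as all randomised participants with an ease-of-application rating for both lenses, whether or not they finish the second wear period or V4. Except those who choose to withdraw their data under section 8, and cross-refer so that the two sections agree. Report the completer analysis as supportive.
2. **Sections 4.4.3 and 4.6.12, unless the redacted steps already cover it:** ask for the rating after the final application attempt, whether or not it succeeds, and record success yes/no. Rating the attempt directly largely avoids having to assign a score.
3. **Reporting:** tabulate failed applications and discontinuations by lens. Participants who stop before the second rating have no pair and stay outside the set in item 1, so this table is where they appear.
4. **Sensitivity analysis only:** score an unrated failed application at the least-easy end of the scale (the visible text does not say which end that is). State this as an exception to the rule against extrapolating missing data.

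The cost is analysis-set wording and one form field, with no additional participants or visits.
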